6.3.1 Withdrawal of IMP

Subjects can decide to discontinue IMP but continue participation in the study. If IMP is. discontinued, the investigator should encourage the subject to continue participation by attending scheduled study visits to have procedures/assessments performed and data collected including endpoints and AEs. The investigator must document any changes to the scheduled visits and assessments (Table 5–1) and the plan for follow up that is agreed by the subject.

Subjects might have IMP withdrawn if any of the following events occur (but not limited to):

- Subject request.
- Decision of the sponsor or investigator.
- Safety concern (eg., due to an AE, ineligibility determined, protocol deviation, noncompliance, requirement for alternative therapy, protocol-specified criteria).
- Clinical fracture or BMD decrease from baseline of 7% or more at the lumbar spine, total hip, or femoral neck.

In the event that a subject experiences a clinical fracture or a BMD decrease from baseline of 7% or more at the lumbar spine, total hip or femoral neck at any time during the study, the investigator is required to discuss the subject's individual fracture risk and alternative treatment options with the subject and to note the discussion in the subject's records. If a decision is made to begin an alternative approved therapy, the subjects must discontinue IMP and every effort should be made to have the subject complete the remaining study visits and assessments.

Withdrawal from study 6.3.2

Subjects can be withdrawn from the study if any of the following events occur:

- Subject develops a serious illness that would interfere with her continued participation.
- Subject is noncompliant with the study procedures or medications in the opinion of the investigator.
- Subject withdraws her consent.
- There is confirmation of a pregnancy during the study, as evidenced by a positive pregnancy test.
- The sponsor or a regulatory agency requests withdrawal of the subject.

Withdrawal of consent for a study means that the subject does not wish to continue in the study. Subject data up to withdrawal of consent will be included in the analysis of the study.

Subjects who withdraw from the study should complete the ET Visit. Refer to the schedule of assessments for the procedures to be performed at this visit (Table 5–1). These subjects will be encouraged to return to the study site to complete the procedures and assessments for the EOS Visit, 4 months after the final administration of IMP.

Investigators should attempt to obtain information on subjects in the case of withdrawal or discontinuation. For subjects considered as lost to follow up, the investigator should make an effort (at least 1 phone call and 1 written message to the subject), and document his/her effort (date and summary of the phone call and copy of the written message in the source documents), to complete the final evaluation. All results of these evaluations and observations, together with a narrative description of the reason(s) for removing the subject, must be recorded in the source documents. The eCRF must document the primary reason for withdrawal.

Subjects who withdraw from the study will not be replaced.

6.3.3 Potential drug-induced liver injury IMP discontinuation criteria

Subjects with potential drug-induced liver injury (PDILI) must be assessed to determine if IMP must be discontinued. In addition, all concomitant medications and herbal supplements that are not medically necessary should also be discontinued.

The PDILI criteria below require immediate and permanent discontinuation of IMP:

- Subjects with either of the following:
 - ALT or AST ≥8xULN
 - ALT or AST ≥3xULN and coexisting total bilirubin ≥2xULN

The PDILI criterion below requires immediate discontinuation of IMP:

• Subjects with ALT or AST ≥3xULN who exhibit temporally associated symptoms of hepatitis or hypersensitivity. Hepatitis symptoms include fatigue, nausea, vomiting, right upper quadrant pain or tenderness. Hypersensitivity symptoms include fever (without clear alternative cause), rash, or eosinophilia (ie, >5%).

If a nondrug-related cause for the symptoms can be confirmed, these subjects may resume IMP administration after discussion with the responsible UCB physician, but only when the requirements for rechallenge with IMP as provided in Section 11.6.1.2.1 are followed.

The PDILI criterion below allows for subjects to continue on IMP at the discretion of the investigator.

• Subjects with ALT or AST $\ge 3x$ ULN (and $\ge 2x$ baseline) and $\le 8x$ ULN, total bilirubin $\le 2x$ ULN, and no eosinophilia (ie, $\le 5\%$), with no fever, rash, or symptoms of hepatitis (eg, fatigue, nausea, vomiting, right upper quadrant pain or tenderness).

Evaluation of PDILI must be initiated as described in Section 11.6.1. If subjects are unable to comply with the applicable monitoring schedule, IMP must be discontinued immediately.

Investigators should attempt to obtain information on subjects in the case of IMP discontinuation to complete the final evaluation. Subjects with PDILI should not be withdrawn from the study until investigation and monitoring are complete. All results of these evaluations and observations, as well as the reason(s) for IMP discontinuation and subject withdrawal (if

applicable), must be recorded in the source documents. The eCRF must document the primary reason for IMP discontinuation.

6.4 Retesting

During the Screening Period, any laboratory values can be retested once to determine subject's eligibility for the study and to ensure that there is no further ongoing clinical relevance.

All retests must be confirmed by the central laboratory and the subject must be randomized within the 35-day Screening Period.

6.5 Lateral spine x-ray at Screening

The x-rays of the lateral thoracic and lumbar spine will be acquired according to specific instructions provided by the central imaging vendor.

For assessment of prevalent vertebral fractures at Screening, which will be performed by a radiologist at the central imaging center, a visual semiquantitative grading scale as defined in Table 6–1 will be used (Genant et al, 1993).

Table 6–1: Semiquantitive	(SQ)	grading scale
---------------------------	------	---------------

Grade	Fracture severity	Definition
0	Normal	Approximately less than 20% reduction in anterior, middle, and/or posterior height
1	Mild	Approximately 20% to 25% reduction in anterior, middle, and/or posterior height
2	Moderate	Approximately 25% to 40% reduction in anterior, middle, and/or posterior height
3	Severe	Approximately 40% or greater reduction in anterior, middle, and/or posterior height

7 STUDY TREATMENT

7.1 Description of investigational medicinal product

For this study, romosozumab and placebo are considered IMP.

Subjects will be administered either romosozumab or placebo in a blinded manner for 6 months after which time, all subjects will receive active treatment (romosozumab) in an OL manner for 6 months.

Romosozumab will be supplied as a sterile, clear to opalescent, colorless to light yellow, preservative-free solution for sc injection in a single-use prefilled syringe (PFS). Each PFS contains 90mg/mL of romosozumab in 55mM acetate and 13mM calcium containing 6.0% w/v sucrose and 0.006% w/v polysorbate 20 at pH 5.2, with a deliverable volume of 1.17mL (105mg romosozumab solution for injection).

Placebo is supplied in a 1.17-mL PFS identical in appearance to romosozumab. Placebo will be stored and packaged the same as romosozumab.

Details of the IMP are provided in the IMP Handling Manual.

Subjects will be required to take daily calcium and vitamin D supplementation during the study; however, these protocol-required products are not considered IMP. Further information on the calcium and vitamin D supplementation is provided in Section 7.8.1.1.

7.2 Treatments to be administered

Procedures for dose administration are provided in the IMP Handling Manual. All IMP will be administered to subjects at the study site by trained study personnel.

The IMP (romosozumab or placebo) will be administered over 2 study periods: the Double-Blind, Placebo-Controlled Period immediately followed by the OL Treatment Period as detailed below.

- Double-Blind, Placebo-Controlled Period
 - Approximately 300 subjects will be randomized, stratified by age (<75 years, ≥75 years), in a 2:1 ratio to receive romosozumab 210mg sc QM (approximately 200 subjects) or matched placebo sc QM (approximately 100 subjects) in a blinded manner for 6 months, with the final administration of double-blind IMP at Month 5.

- OL Treatment Period
 - At Month 6, all subjects will receive romosozumab 210mg sc QM for 6 months in an OL fashion, with the final administration of OL romosozumab at Month 11.

Subjects will receive 2 sc injections of romosozumab QM (ie, 2 injections of 105mg romosozumab for a total dose of 210mg) or 2 injections of matched placebo QM for 6 months during the Double-Blind, Placebo-Controlled Period. The 2 sc injections will be administered one immediately after the other. During the OL Treatment Period, all subjects will receive 2 sc injections of romosozumab QM (ie, 2 injections of 105mg romosozumab each administered one immediately after the other for a total dose of 210mg) for 6 months. A separate 1.17-mL PFS will be used for each injection. Thus, to administer the IMP at each dosing visit, 2 PFS (romosozumab or placebo) will be supplied in a single box.

Injections will be administered sc into different sites on the subject's anterior abdominal wall, upper thigh, or upper arm by an individual at the study site who has been trained in the injection technique. The injection should not be administered in the same arm from which blood is drawn. The IMP injections must be administered after all other study visit procedures have been completed.

The first dose of IMP must be administered on the day of randomization (Day 1). Details of the IMP administered including the date and time are to be recorded on each subject's eCRF.

Over the course of the study, a physician must be available during administration of romosozumab or placebo. It is recommended that all subjects be closely observed for approximately 30 minutes after dosing. In the unlikely event of overdose, refer to Section 11.4 for further information.

7.3 Packaging

The IMP will be manufactured, packaged, and labeled according to Good Manufacturing Practice (GMP) guidelines and applicable laws or regulations. The IMP will be suitably packaged in such a way as to protect it from deterioration during transport and storage.

Romosozumab and placebo injections will be identical in appearance and will be presented in indistinguishable containers (PFS) and boxes during the Double-Blind, Placebo-Controlled Period. The 2 PFS required for each IMP administration will be supplied in a single box, as assigned by the interactive response technology (IRT) system.

7.4 Labeling

Clinical drug supplies will be labeled in accordance with the current ICH guidelines and Good Clinical Practice (GCP) and GMP and will include any locally required statements. If necessary, labels will be translated into the local language.

7.5 Handling and storage requirements

Refer to the IMP Handling Manual for the storage conditions of the IMP.

The investigator (or designee) is responsible for the safe and proper storage of IMP at the site. Investigational medicinal product stored by the investigator is to be kept in a secured area with limited access according to the storage conditions mentioned on the label.

Appropriate storage conditions must be ensured either by controlling the temperature (eg, room, refrigeration unit) or by completion of a temperature log in accordance with local requirements on a regular basis (eg, once a week), showing actual and minimum/maximum temperatures reached over the time interval.

In case an out-of-range temperature is noted, it must be immediately reported as per instructions contained in the IMP Handling Manual.

7.6 Drug accountability

A Drug Accountability form will be used to record IMP dispensing information on a by-subject basis and will serve as source documentation during the course of the study. Details of any IMP lost, damaged (due to breakage or wastage), not used, partially used, disposed of at the study site, or returned to the sponsor or designee must also be recorded on the appropriate forms. All supplies and pharmacy documentation must be made available throughout the study for UCB (or designee) to review.

To administer the injections, study personnel must be appropriately trained and licensed (per country guidelines).

The investigator (or designee) is responsible for retaining all used, unused, and partially used containers of IMP until returned or destroyed.

The investigator may assign some of the investigator's duties for drug accountability at the study site to an appropriate pharmacist/designee.

The investigator must ensure that the IMP is used only in accordance with the protocol.

After completion of the clinical phase of the study, all used (including empty containers)/partially used, unused, damaged, and/or expired IMP must be reconciled and either destroyed at the site according to local laws, regulations, and UCB Standard Operating Procedures (SOPs) or returned to UCB (or designee). Investigational medicinal product intended for the study cannot be used for any other purpose than that described in this protocol.

7.7 Procedures for monitoring subject compliance

The IMP will be administered at the study site by staff trained in the injection technique. Date and time of IMP administration will be recorded in the subject's eCRF. Drug accountability must be recorded on the Drug Accountability form.

Any treatment administered from the time of signing the ICF to the EOS Visit will be considered concomitant medication. This includes medications that were started before the study on a ongoing during the study.

Any concomitant medication use reported by the subject during the study will be recorded in the eCRF.

Permitted concomitant treatments (medications and therapies) 7.8.1

Throughout the study, the investigator may prescribe any concomitant medications or treatments deemed necessary to provide adequate supportive care except for those listed in Section 7.8.2.

Subjects taking concomitant Chinese herbal medication as indicated by the investigator for osteoporosis must be on a stable dose prior to study entry and continue on that dose throughout the study.

7.8.1.1 Calcium and vitamin D supplementation

All subjects will be required to take daily calcium and vitamin D supplementation by the oral route during the study. Details of daily calcium and vitamin D supplementation are to be recorded in the subject's eCRF.

The calcium and vitamin D supplements are not considered IMP. The investigator will be responsible for ensuring that subjects have access to these protocol-required therapies. Where available, vitamin D₃ preparations should be used; if vitamin D₃ is not available, use of vitamin D₂ preparations is acceptable.

From Screening through the EOS Visit, subjects should be taking between 500 to 600mg of elemental calcium along with 800 to 1200IU of vitamin D daily.

Subjects with a serum 25 (OH) vitamin D level of ≥20ng/mL and ≤40ng/mL at Screening will receive an initial loading dose of 50,000IU of vitamin D on Day 1 (or within 1 week of Day 1) by the oral route. Subjects with a serum 25 (OH) vitamin D level of >40ng/mL at Screening may also receive the vitamin D loading dose at the investigator's discretion. Subjects whose serum 25 (OH) vitamin D at Screening is <20ng/mL may be given vitamin D supplementation and retested once during the Screening Period to determine subject's eligibility.

If a subject develops hypercalcemia over the course of the study, the investigator may use his or her medical judgment and reduce the calcium and/or vitamin D supplementation to maintain serum calcium concentration within the normal range. If a subject develops hypocalcemia over the course of the study, appropriate additional supplementation should be instituted as deemed acceptable by local guidelines, to maintain serum calcium concentration within the normal range. If a subject is unable to tolerate the daily calcium or vitamin D supplementation, the formulation may be changed or the dosage lowered. The intolerance as well as the resolution (ie, change in formulation or dosage) should be documented in the subject's chart.

Confidential Page 47 of 108

7.8.2 Prohibited concomitant treatments (medications and therapies)

Chinese herbal medicine for treating osteoporosis must not be initiated at any time during the study.

In addition, the following concomitant medications are prohibited until the end of the OL Treatment Period (Month 12 Visit) or until 1 month after the early termination of study medication:

- Strontium (including strontium ranelate and over-the-counter strontium preparations)
- Fluoride
- Vitamin K and vitamin K analogs (for the treatment of osteoporosis)
- Activated vitamin D (1,25-di[OH] vitamin D or 1 [OH] vitamin D)
- iv bisphosphonates
- Oral bisphosphonates (cumulative dosing regimens of ≤1 month are acceptable)
- Denosumab
- TPTD or any PTH analogs
- Systemic oral or transdermal estrogen (cumulative dosing regimens of ≤ 1 month are acceptable; vaginal preparations and estrogen creams will be allowed at any time)
- SERMs (cumulative dosing regimens of ≤1 month are acceptable)
- Calcitonin (cumulative dosing regimens of ≤1 month are acceptable)
- Tibolone
- Prolonged (ie, >3 months) oral glucocorticoid therapy at a prednisone equivalent dose of ≥5.0mg/day (tapering glucocorticoid courses of ≤1-month duration is permitted regardless of dose; inhaled or topical glucocorticoids are permitted)
- Any cathepsin K inhibitor, such as odanacatib (MK-0822)
- Hormonal ablation therapy
- Cinacalcet

7.8.3 Rescue medication

No alternative osteoporosis medication will be allowed during this study and no change in the dose and frequency of romosozumab administration is permitted. In the event that a subject experiences a clinical fracture during the study, the investigator may discuss alternative treatment options. If the decision is made to begin an alternative approved therapy, the subject must discontinue IMP. Every effort should be made to have the subject complete the remaining study visits and assessments.

7.9 Blinding

This is a Phase 3 multicenter, randomized, 6-month double-blind, placebo-controlled study followed by a 6-month OL Treatment Period. Details on maintaining the blind during the

Double-Blind, Placebo-Controlled Period and minimizing any bias during the OL Treatment Period are provided in Section 7.9.1.1 and Section 7.9.1.2, respectively.

7.9.1 Procedures for maintaining and breaking the treatment blind

7.9.1.1 Double-Blind, Placebo-Controlled Period

All IMP injections administered during the Double-Blind, Placebo-Controlled Period (romosozumab and placebo) will be identical in appearance, presented in identical containers (PFS), and stored and packaged in the same manner in order to maintain the blind.

All sponsor, contract research organization (CRO), and investigator site personnel involved in the study will be blinded to the IMP assignment during the Double-Blind, Placebo-Controlled Period with the following exceptions:

- Sponsor Patient Safety (PS) staff reporting SAEs to regulatory authorities
- Bioanalytical laboratory staff (analyzing blood samples for PK, antibodies, and BTMs)
- Unblinded CRO Randomization Biostatistician (to produce the randomization list)
- Unblinded Medical Monitor (only when deemed necessary to provide appropriate medical care to a subject)

7.9.1.2 Open-Label Treatment Period

After the last subject has completed the final visit in the Double-Blind, Placebo-Controlled Period, individuals at the sponsor and CRO who will be involved in the data management and data cleaning, statistical analysis of the 6-month double-blind data, and the writing of the associated Clinical Study Report (CSR), will be unblinded to initial IMP assignments. Upon finalization of the CSR (6-month analysis), investigators will be unblinded to subject level treatment assignments. Investigators are obliged not to disclose to subjects their initial IMP assignment so that subjects will remain blinded during both the Double-Blind, Placebo-Controlled and OL Treatment Periods of the study.

7.9.1.3 Maintenance of study treatment blind

All subject treatment details (romosozumab and placebo) will be allocated and maintained by the IRT system.

Under normal circumstances, the blinded treatment must not be revealed. In the case of a medical emergency, UCB or its representatives must be notified immediately if the blind is broken.

7.9.1.4 Breaking the treatment blind in an emergency situation

The integrity of the clinical study must be maintained by observing the treatment blind. In the event of an emergency, it will be possible to determine to which treatment arm the subject has been allocated by contacting the IRT system. All sites will be provided with details of how to contact the system for code breaking at the start of the study. The Medical Monitor or equivalent should be consulted prior to unblinding, whenever possible.

The Clinical Project Manager (CPM) will be informed immediately via the IRT system when a code is broken, but will remain blinded to specific treatment information. Any unblinding of the

IMP performed by the investigator must be recorded in the source documents and on the Study Termination eCRF page.

7.10 Randomization and numbering of subjects

An IRT system will be used for assigning subjects to treatment based on a predetermined production randomization list provided by the CRO. A CRO Randomization Biostatistician who is not involved otherwise in the study will write the randomization code using a validated program and produce the randomization list. The randomized list will be retained at the CRO in a secure location until database lock. The CRO team and UCB team directly involved in the conduct of the study will not have access to the productive randomization list up to the unblinding of the study. Before the start of the study, copies of the randomization list will be sent in a secure fashion to the IRT system and to the unblinded personnel identified in Section 7.9.1.1. The IRT system will generate individual assignments for subject kits of IMP, as appropriate, according to the visit schedule.

Subjects will be randomized, stratified by age (<75 years, ≥75 years), in a 2:1 ratio of romosozumab to placebo during the Double-Blind, Placebo-Controlled Period, after which, all subjects will receive romosozumab during the OL Treatment Period.

At Screening (Visit 1), after signing the ICF, the investigator or designee will contact the IRT system to enter a subject in the study. Each subject will be assigned a 5-digit number via the IRT system that serves as the subject identifier throughout the study. The subject number will be required in all communication between the investigator or designee and the IRT system regarding a particular subject.

To randomize a subject to treatment on Visit 2 (Day 1), the investigator or designee will contact the IRT system to obtain the subject's randomization number. The randomization number must be incorporated into the subject's eCRF.

The IRT system will allocate kit numbers based on the subject number for both the Double-Blind, Placebo-Controlled Period and the OL Treatment Period. Subject number and kit numbers will be tracked via the IRT system.

The investigator or designee will contact the IRT system when a subject discontinues IMP and/or discontinues the study. Subjects who withdraw from the study will not be replaced.

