 - If subject has >ULN ALT, AST, or ALP that does not meet the exclusion limit at Screening, repeat the tests, if possible, prior to dosing to ensure there is no further ongoing clinically relevant increase. In case of a clinically relevant increase, inclusion of the subject must be discussed with the Medical Monitor.
- 21. Subject is currently receiving treatment in another investigational device or drug study, or less than 30 days or 5 half-lives (whichever is longer) since ending treatment on another investigational device or drug study(ies).
- 22. Subject is undergoing other investigational procedures while participating in this study.
- 23. Subject has previously entered this study or has previously participated in a study with a sclerostin antibody product.
- 24. Subject has had a malignancy within the last 5 years, except nonmelanoma skin cancers, cervical or breast ductal carcinoma in situ.
- 25. Subjects has a known hypersensitivity to any of the products to be administered during dosing (calcium supplements, vitamín D products, or mammalian cell derived products).
- 26. Subject who is breastfeeding or plans to become pregnant or breastfeed during the study or within 12 weeks of the final dose of study drug.
- 27. Subject has a history or evidence of any other clinically significant disorder, condition or disease (eg, untreated or unstable, with the exception of those outlined above) that, in the opinion of the investigator, if consulted, would pose a risk to subject safety or interfere with the study evaluation, procedures, or completion.
- 28. Subject shows a positive result for human immunodeficiency virus (HIV), hepatitis C virus, or hepatitis B infection at Screening (Visit 1).
- 29. Subject has an active tuberculosis infection within 6 months of signing the ICF.
- 30. Subject has active pneumonia.
- 31. Subject has a reported history of hearing loss associated with cranial nerve VIII compression due to excessive bone growth (eg, as seen in conditions such as Paget's disease, sclerosteosis, and osteopetrosis).

Withdrawal criteria 6.3

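### Protocol 7.10, read literally, gives the randomization list before study start to a Medical Monitor and sponsor safety staff who need only single-subject codes

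*Protocol*

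**What the plan says.** Protocol 7.10 first sets a bar: "The CRO team and UCB team directly involved in the conduct of the study will not have access to the productive randomization list" until the study is unblinded, and the list is kept secure at the CRO until database lock. It then sets a distribution rule: before the study starts, "copies of the randomization list will be sent in a secure fashion to the IRT system and to the unblinded personnel" named in Section 7.9.1.1.

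Section 7.9.1.1 names four exceptions to the blind:

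- "Sponsor Patient Safety (PS) staff reporting SAEs to regulatory authorities";
- bioanalytical laboratory staff;
- the CRO Randomization Biostatistician, who produces the list;
- "Unblinded Medical Monitor (only when deemed necessary to provide appropriate medical care to a subject").

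Section 7.9.1.4 gives a separate route for one subject: the treatment arm is obtained from the IRT, the Clinical Project Manager is told at once that a code was broken but not what it was, and any unblinding by the investigator is recorded.

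The SAP is silent on who holds the list.

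**The concern.** A role that may be unblinded only when one subject's care requires it should not hold a copy of the list before anyone has been randomized. Reporting an SAE likewise needs the assignment of the affected subject, not of all subjects and not of those still to come.

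These roles are not remote from trial decisions. A Medical Monitor is consulted on some inclusions (6.2: "inclusion of the subject must be discussed with the Medical Monitor"), on withdrawals (6.3) and on liver events (11.6.1.1). Patient Safety works with the Study Physician on SAE reconciliation (11.5). What is at stake is an avoidable route by which knowledge of treatment could reach discussions about inclusion, discontinuation and adverse events in the double-blind period.

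**Working it through.** No arithmetic applies. The check sets the sections side by side.

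**1. Who receives the list.** 7.10 points to all unblinded personnel in 7.9.1.1. It exempts no role and specifies no subset of the list. Read literally, all four roles are recipients.

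**2. When.** The sentence opens "Before the start of the study, copies of the randomization list", so distribution precedes the first randomization and the copies cover assignments not yet made.

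**3. Need, role by role.**

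| Role in 7.9.1.1 | Need for the list | Conflict |
|---|---|---|
| CRO Randomization Biostatistician | Writes it | None |
| Bioanalytical laboratory | Plausible: 11.7.5 tests antibodies only in samples from subjects who receive romosozumab | None |
| Sponsor Patient Safety | Single assignments, for SAE reporting | Exceeds the stated purpose; whether it also breaks the 7.10 bar is arguable |
| Unblinded Medical Monitor | Single assignments, when care requires | Direct conflict with the 7.9.1.1 condition |

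**4. Is the list needed for emergencies?** No. 7.9.1.4 already supplies single-subject codes through the IRT, with notification. Reading a copied list triggers no such notice.

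**5. What can a holder learn?** 7.10 requires the randomization number to be entered in the eCRF. A holder who also had eCRF access could decode subjects already randomized. Predicting the next subject is harder, because it requires knowing which entry the IRT will issue next, and the documents give no listed role that live information.

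**6. Is site-level concealment affected?** No. The site contacts the IRT on Day 1 for the randomization number (7.10, 8.2.1) and is not a recipient.

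**7. Is the endpoint affected?** DXA scans are analyzed by the central imaging vendor, and results are withheld from sites after the first dose (10.1). No listed role reads scans.

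**8. Comparison with other safeguards.** 11.6 withholds potentially unblinding laboratory results from study-related personnel after Day 1. 13.7 requires an independent group outside study conduct when the DMC needs unblinded data. The list distribution is looser than both.

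**The case against.** The strongest reply is that 7.9.1.1 is a general rule with listed exceptions, which is not a contradiction, and that the Medical Monitor's condition travels with the cross-reference. On that reading nobody meets the condition before study start, so no list is sent to that role. The reading is possible, but 7.10 does not state it, and the label in 7.9.1.1 describes the monitor as already unblinded.

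Second, the Unblinded Medical Monitor may be a different person from the Medical Monitor in 6.2, 6.3 and 7.9.1.4. The last of these is consulted before a code is broken, which suits a blinded person. The protocol does not settle this. Separate people would remove most of the inclusion and withdrawal concern, but not the conflict between 7.10 and 7.9.1.1.

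Third, the openings for bias are narrow, and this stands. The inclusion discussion in 6.2 arises only for liver tests above normal but below the exclusion limit that show a clinically relevant increase on repeat. Numeric criteria govern much of the liver-event handling (6.3.3, Table 11-3). Investigators assess SAE causality while the sponsor assesses expectedness (11.1.2.3). Jaw, femoral and cardiovascular events go to blinded adjudication (SAP 10.2.4.1 to 10.2.4.3).

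A reader might infer that allocation concealment is broken, or that all of the approximately 300 assignments are exposed subject by subject from the outset. The documents do not support that: sites have no list, and before randomization no entry is linked to a subject. Nor do they show that 7.10 plainly breaches its own bar for Patient Safety staff, since it is unclear whether they count as directly involved in conduct.

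**Conclusion.** The point holds as a weakened safeguard, not a demonstrated breach. The firmest part is the Medical Monitor: a condition tied to one subject's care in 7.9.1.1 cannot be squared with an advance copy under 7.10. The Patient Safety part rests on need: the stated purpose does not call for the list.

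The exposure is confined to inclusion discussions, discontinuation and adverse event handling during the double-blind period. No effect on the primary or secondary BMD measurements follows from the text, and the documents give no basis for sizing any bias.

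The conclusion assumes the literal reading of 7.10 and that no other study document narrows the distribution. If the Unblinded Medical Monitor and the consulted monitor are one person, the concern is stronger; if they are separate, it reduces to an access rule that goes beyond need. Either way, a small correction is worth making.

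**What to change.** Reword 7.10 to name the holders of the list: the IRT, the CRO Randomization Biostatistician who produces it and, if antibody testing needs it, the bioanalytical laboratory. State that Patient Safety and the Medical Monitor obtain single-subject codes through the IRT with an audit trail. State that any Unblinded Medical Monitor is a different person from the monitor consulted on inclusion and withdrawal.

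Rewording cannot recall copies already sent. The protocol is at Amendment 3 and the 2023 SAP describes procedures already disrupted by COVID-19, so distribution may have taken place. In that case, document who received the list, when, and what part each recipient had in inclusion, withdrawal or adverse event decisions.

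The cost is a few sentences of amendment, IRT role settings and a record of recipients. Sample size, data collection and analysis are unchanged.
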